#### 4.5 Subject Recruitment Status

#### 4.5.1 Participation Status of Clinical Study and Dropout Subjects

The screening status and reasons for screening failure shall be presented for the recruited subjects, and the number of subjects shall be presented for the enrollment status in the clinical study. The number of subjects and percentages shall be summarized and presented for the clinical study completion and drop-out status, and a list shall be presented for the subjects dropped out. At this time, the screening status and the reasons for screening failure shall be shown in a schematic diagram.

#### 4.5.2 Status of Analysis Set

The number of subjects and percentages shall be summarized and presented for the inclusion status of the analysis set and the reasons for exclusion.

#### 4.5.3 Protocol Deviations

For subjects who completed the clinical study but were excluded from the analysis set due to protocol violations, the reasons for violation shall be presented as a list.

- · Major protocol deviations shall be presented based on the ITT set.
- Major protocol deviations related to COVID-19 shall also be presented based on the ITT set.

#### 4.6 Demographic Information and Comparison of Clinical Characteristics

#### 4.6.1 Demographic Information

Descriptive statistics (number of subjects, mean, standard deviation, median, minimum, maximum) shall be presented for continuous variables (age, height, weight, BMI), while frequencies and percentages shall be presented for categorical variables (sex, smoking history, alcohol consumption history).

#### 4.6.2 Medical History Survey (past medical history/current illness)

The number of subjects, percentages, 95% confidence interval (Clopper-Pearson Confidence Interval), and number of cases with past medical history and current illness shall be presented. In addition, past medical history and current illness shall be classified with the system organ classes (SOCs) and preferred terms (PTs) according to the medical dictionary for regulatory activities (MedDRA, V24.0), and the number of subjects, percentages, and number of cases shall be presented.

#### 4.6.3 Previous/Concomitant Medications (Treatment)

The number of subjects, percentages, 95% confidence interval (Clopper-Pearson Confidence Interval), and number of cases shall be presented for prior and concomitant medications. In addition, the number of subjects, percentages, and number of cases shall be presented for prior and concomitant medications by classifying into anatomical main groups and therapeutic subgroups according to the ATC code (Anatomical Therapeutic Chemical classification System, 2021) of the WHO Drug Dictionary.

The number of subjects, percentages, 95% confidence interval (Clopper-Pearson Confidence Interval), and number of cases shall be presented for prior and concomitant treatments. In addition, prior and concomitant treatments shall be classified with the system organ classes (SOCs) and preferred terms (PTs) according to the medical dictionary for regulatory activities (MedDRA, V24.0), and the number of subjects, percentages, and number of cases shall be presented.

#### 4.6.4 Physical Examination

For each physical examination item of the subjects, the frequencies and percentages shall be presented for clinically significant abnormalities (Normal / NCS [Not Clinically Significant Abnormal] / CS [Clinically Significant Abnormal]). In addition, a detailed list shall be presented for clinically significant abnormal results (CS) from physical examinations.

#### 4.6.5 Electrocardiogram

For the electrocardiogram of the subjects, the frequencies and percentages shall be presented for clinically significant abnormalities (Normal / NCS [Not Clinically Significant Abnormal] / CS [Clinically Significant Abnormal]). In addition, a detailed list shall be presented for clinically significant abnormal results (CS) from electrocardiograms.

#### 4.7 Safety and Tolerability Assessments

#### (1) Adverse events

Summarization and analysis of adverse events shall be performed on treatment-emergent adverse events (TEAEs).

The number of subjects, percentages, 95% confidence interval (Clopper-Pearson Confidence Interval), and number of cases shall be presented for treatment-emergent adverse events (TEAEs), adverse drug reactions (ADRs), adverse events of special interest (AESIs), and serious adverse events/adverse drug reactions (SAEs). In addition, the number of subjects, incidence, and number of cases shall be presented for SAE status of adverse events, SAE reason, severity, causal relationship to the investigational product, relationship to the IP administration procedure, relationship to underlying disease, actions related to the investigational product, corrective treatments, outcomes, etc.

The adverse events, adverse drug reactions, and serious adverse events shall be encoded using the system organ classes (SOCs) and preferred terms (PTs) by using the medical dictionary for regulatory activities (MedDRA, V24.0). The number of subjects with onset, the incidence, the number of cases, etc., shall be presented for the encoded adverse events. In addition, a detailed list shall be presented if serious adverse events occur.

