5.1 Purpose of Clinical Study

To evaluate the safety and tolerability of the investigational product (VM202) injected in the weakened lower limb muscles of CMT1A patients.

Primary Objective

To evaluate safety and tolerability following repeated doses of the investigational product (VM202).

Secondary Objectives

To evaluate efficacy following repeated doses of the investigational product (VM202).

- (1) Changes in severity of disease
 - CMTNS-v2 (Charcot-Marie-Tooth Neuropathy Score version 2)
- FDS (functional disability scale)
- (2) Changes in lower limb function:
 - ONLS (overall neuropathy limitation score) leg scale
 - 10MWT (10-meter walk test)
- (3) Changes in fatty infiltration level of lower limb muscles:
 - MRI leg
- (4) Nerve regeneration potential:
 - CMAP (compound motor nerve action potential)
 - SNAP (compound sensory nerve action potential)
 - NCV (nerve conduction velocity)
- (5) HGF antibody generation by VM202

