5.2 Clinical Study Design

[figure not shown]

Figure 7. A schematic diagram of clinical study

This is a phase 1/2a, open-label, single-center study to evaluate for 270 days the safety and tolerability of intramuscularly injected VM202 in twelve CMT1A patients with symptoms of lower limb weakening. When subjects who have voluntarily signed the informed consent form are enrolled in this clinical study, they shall undergo tests to determine their eligibility for this clinical study.

Subjects who have satisfied the inclusion/exclusion criteria shall be given the investigational product 4 times (2 administration sessions for 2 weeks followed by a 3-month safety and tolerability assessment, and then 2 administration sessions for 2 weeks) in total for 104 days. Safety and tolerability assessments shall be performed at every visit, and efficacy assessments shall be performed at the 2nd visit (baseline, Day 0, prior to administration) and the 7th visit (termination visit, Day 270).

Although this is a phase 1/2a clinical study, it is intended to evaluate clinically meaningful endpoints in relation to efficacy considering that Charcot-Marie-Tooth disease type 1A (CMT1A) is a rare disease that still does not have an available treatment method.

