- 13) MRI leg: The muscles of lower limbs shall be imaged, and the fatty infiltration level of the leg muscles injected with the investigational product shall be measured and evaluated as fat content value (%) at one level for each muscle. Considering the schedule, etc., of the institution, it shall be performed optionally at the early termination visit, and if it is not performed, the reasons shall be recorded in the case report form.
- 14) Adverse event assessment: At Visits 3, 4, and 5, an assessment of adverse events that have occurred since the last visit shall be performed prior to administering the investigational product, and localized adverse events shall be assessed at 2 ± 1 hours after administering the investigational product, as well as on the day after administration.
- 15) Hospitalization: Subjects shall be hospitalized on the day before administration of the investigational product and their vital signs shall be measured. If they are not hospitalized, vital signs may be omitted, and the hospitalization day in the case report form shall be recorded the same as the test day prior to administration.
- 16) After administration: Vital signs and adverse events shall be assessed at 2 ± 1 hours after administering the investigational product. The presence or absence of localized adverse events shall be verified on the day after administering the investigational product.

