7.4.3 Reporting, collection, and recording of AEs

The principal investigator must educate the sub-investigator and subjects or representatives of the subject about all adverse events that may occur after the administration of the investigational product and educate them to report all reactions that occur after administration.

- All AEs that occur from administration of investigational product to follow-up visits (until end of the clinical trial) are collected. However, if a sign, symptom, or disease that occurred before the administration is worsened after the administration, it shall also be considered an AE.
- An AE must be reported including the name of the AE, start date and end date, severity, actions related to investigational product, progress, causality with the investigational product, remedial treatment, and whether it is an SAE.
- When documenting an AE, the investigator uses a comprehensive diagnosis or symptom name using standard medical terminology instead of each symptom or sign.
- 4) AEs are observed for the study period of nine months (day 0 to 270). If an AE or SAE that occurs within the nine-month follow-up period is not resolved within this period, follow-up shall be conducted until the AE is resolved.

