8.4.3 Primary Endpoints

(1) Adverse events

: Summarization and analysis of adverse events shall be performed on treatmentemergent adverse events (TEAEs).

The frequencies and percentages shall be presented for the occurrence of treatmentemergent adverse events (TEAEs), adverse drug reactions (ADRs), serious adverse events (SAEs) and adverse events of special interests(AESIs), etc.

The adverse events, adverse drug reactions, and serious adverse events shall be encoded using the system organ classes (SOCs) and preferred terms (PTs) according to the latest

version of the medical dictionary for regulatory activities (MedDRA). The number of subjects with onset, the incidence, the number of cases, etc., shall be presented for the encoded adverse events.

(2) Laboratory tests and vital signs

: For continuous variables, descriptive statistics (mean, standard deviation, median, minimum, maximum) shall be presented for each visit. Frequencies and percentages shall be presented for categorical variables. The frequencies and percentages for normal shifts, not clinically significant (NCS) abnormal shifts, and clinically significant (CS) abnormal shifts shall be presented for each visit. The subjects who have been assessed as clinically significant (CS) at each visit shall be presented in a list.

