#### 1.4 Number of Subjects

#### 1.4.1 Target Number of Subjects and Rationale for Calculation

Using this investigational product, clinical studies have been conducted on six diseases in total since 2007. Although there were no cases in which the drug was applied to CMT1A patients, a total of 18 subjects were recruited in a clinical study on amyotrophic lateral sclerosis among these studies. As a result of assessing safety, it was intended that this clinical study be conducted with 12 subjects considering the addition of indication and the slow progression of disease even though this clinical study also targets similar symptoms.

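### The planned adverse event tables have no breakdown by administration, so they cannot separate reactions that fade after dose 1 from reactions that first appear on re-administration

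*SAP*

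**What the plan says.** **Objective and design.** Protocol 5.1 gives the primary objective as "To evaluate safety and tolerability following repeated doses of the investigational product (VM202"). Under Protocol 5.2, subjects "shall be given the investigational product 4 times", in two courses of two sessions (Days 0 and 14, then Days 90 and 104). On sample size, SAP 1.4.1 says "it was intended that this clinical study be conducted with 12 subjects".

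**Adverse event output.** SAP 4.7(1) states: "The number of subjects, percentages, 95% confidence interval (Clopper-Pearson Confidence Interval), and number of cases shall be presented for treatment-emergent adverse events (TEAEs"), with the same summary for ADRs, AESIs and SAEs. It then adds tables by event attribute: seriousness, severity, causality, and on to "relationship to the IP administration procedure, relationship to underlying disease, actions related to the investigational product, corrective treatments, outcomes, etc". Coding to SOC and PT follows. A detailed listing is promised only for serious events. Protocol 8.4.3 is equivalent: "The number of subjects with onset, the incidence, the number of cases, etc., shall be presented for the encoded adverse events". The subgroups in SAP 2.3 and 4.9 are all subject characteristics. None of these places mentions dose, course, visit or interval.

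**The other primary safety items.** SAP 4.7(2) and (3) summarise laboratory tests and vital signs by visit. Vital signs are also compared before and after administration.

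**What is collected.** Protocol 7.4.3 requires a start and end date for every AE and says "AEs are observed for the study period of nine months (day 0 to 270"). Footnote 14 of the schedule in Protocol 6.1 adds that "localized adverse events shall be assessed at 2 ± 1 hours after administering the investigational product, as well as on the day after administration"; sections 6.1.2.3, 6.1.3.3, 6.1.5.3 and 6.1.6.3 apply this check after each of the four sessions. Protocol 7.2.2 defines an injection site reaction as one seen within 24 hours of the injection, and Protocol 7.4.3.1 makes these reactions an AESI.

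**Exposure.** SAP 4.5.1 reports completion and drop-out. No visible section tabulates how many doses subjects received.

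**The concern.** The feature of this design is re-administration: a second dose after two weeks, then a second course after a gap of about three months. The earlier ALS experience cited in Protocol 3.9 used four doses one week apart, so it does not speak to that longer gap. A reader of the final report will want to know whether local reactions settle after the first session, stay level, or begin when the product is given again.

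The planned AE tables summarise each subject once per event class and add a total case count. Opposite time patterns can produce identical tables. Non-serious injection site reactions have no planned listing either, so nothing in the visible plan would show their timing.

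There is also a smaller denominator issue. The safety set includes anyone dosed and assessable. If some subjects miss later doses, a percentage of the whole set understates the frequency among those who actually received them, and no exposure table would reveal it.

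**Working it through.** The plan states no event rate, precision or power to reproduce; 12 subjects is justified only by reference to the 18-subject ALS study. The calculations below are illustrative and use the SAP's own Clopper-Pearson method.

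**1. What the planned table can distinguish.** Assume 6 of 12 subjects have one reaction each. The limits are the 2.5% point of Beta(x, n − x + 1) and the 97.5% point of Beta(x + 1, n − x).

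| Pattern | Reactions at dose 1/2/3/4 | Planned output | By session |
|---|---|---|---|
| Fades after dose 1 | 6/0/0/0 | 6/12 = 50% (21.1 to 78.9%), 6 cases | 50% (21.1 to 78.9%), then 0% (0 to 26.5%) three times |
| Appears at dose 4 | 0/0/0/6 | the same | 0% (0 to 26.5%) three times, then 50% (21.1 to 78.9%) |
| Flat | 2/1/1/2 | the same | 2/12: 2.1 to 48.4%; 1/12: 0.2 to 38.5% |
| Second course only | 0/0/3/3 | the same | 0/12 twice, then 3/12 = 25% (5.5 to 57.2%) twice |

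For 0/12 the upper limit is 1 − 0.025^(1/12) = 26.5%. Event attributes and SOC/PT could also be identical across the four patterns.

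**2. Can a reaction be assigned to a dose?** For injection site reactions, yes. The definition spans 24 hours and the shortest nominal gap between sessions is 14 days.

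**3. Other events.** The nominal time after each dose is 14 − 0 = 14, 90 − 14 = 76, 104 − 90 = 14 and 270 − 104 = 166 days. If each event were assigned to the most recent dose, a constant background rate would give dose 4 about 166/14 = 11.9 times the events of dose 1, and course 2 (270 − 90 = 180 days) twice those of course 1 (90 days). That rule would create a rise on re-administration where none exists.

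**4. Incomplete dates.** SAP 4.3 sets an unknown start day to the 1st of the month, with an exception only for the month of Day 0, where it becomes Day 0. An event that followed dose 2, 3 or 4 can therefore be dated before that dose.

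**5. Denominator.** The documents give no drop-out rate. Suppose 3 subjects have an event after course 2. On the full set that is 3/12 = 25%. If 0, 2 or 4 subjects (assumed) had stopped before dose 3, the frequency among those exposed would be 25%, 3/10 = 30% or 3/8 = 37.5%.

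**6. Should doses be tested against each other?** An exact two-sided McNemar test with m discordant subjects all in one direction gives p = 2 × 0.5^m: 0.0625 for m = 5 and 0.031 for m = 6. At least 6 of the 12 would have to change the same way. For dose 1 against dose 4, under assumed rates of new onset and resolution, power is 4% at 25%/5%, 23% at 40%/5% and 42% at 50%/5%. It reaches 84% only in the extreme case of 60%/0%.

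**The case against.** **The SAP text is incomplete.** Its contents page lists sections 5 to 7 after 4.9. These are not in the available text, and the section 5 heading is not legible. If they hold table shells, a by-dose or exposure table could be there. This stands, and it limits the point to the visible text.

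**The plan is richer than one incidence.** Case counts, severity, causality, relationship to the procedure and action taken are all planned, and the attribute list is open-ended. SAP 4.1 also promises a descriptive comparison of treatment and follow-up periods. This is true, but none of it separates doses 1 to 4. The 4.1 statement is not carried into 4.7(1), and an open-ended list pre-specifies nothing.

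**No objective asks for a comparison between doses.** Cumulative incidence over 270 days is a legitimate answer to the study title, and Protocol 3.9 explains the 90-day interval by residual product, not by a re-exposure hypothesis. This also stands: the planned table is a valid summary that leaves out a useful second view.

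**Cells are too small.** With 12 subjects per dose the table cannot establish a trend. That argues against testing, not against showing the counts.

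**A stronger reading.** A reader might infer that the trial itself cannot show how reactions change with repeated dosing. The documents do not support that: onset dates and local checks after every session are collected, and laboratory tests and vital signs are analysed by visit.

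**Conclusion.** The point holds for the planned output. As visible, SAP 4.7(1) and Protocol 8.4.3 contain no AE summary by administration and no summary of doses received. The planned AE tables therefore cannot distinguish reactions that fade after dose 1 from reactions that first appear on re-administration. In the worked case, four different patterns over up to 12 × 4 = 48 dose exposures all reduce to 6/12 (21.1 to 78.9%) and 6 cases.

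The six events in that case are an assumption, chosen to show that the tables coincide; they do not predict a rate. The denominator effect also rests on assumed drop-out and is small beside the interval for 3/12 (5.5 to 57.2%).

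A reader might also set the cumulative incidence against a per-session risk and call the ratio a bias. At an assumed 30% per session with independence, 1 − 0.7^4 = 76%, or 2.5 times 30%. These are different quantities, each valid for its own question, and independence within a subject is unlikely, so the ratio measures no error.

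This is a cheap improvement worth making before data lock. It does not invalidate the planned safety analysis.

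**What to change.** Add to SAP 4.7(1), after checking that sections 5 to 7 do not already provide it:

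> Injection site reactions will be tabulated by session (dose 1, 2, 3, 4), using the 24-hour definition in Protocol 7.2.2. The denominator is the number of subjects dosed at that session. An exposure table will give the number of subjects who received 1, 2, 3 and 4 doses and the cumulative amount given. These tables are descriptive; no tests between doses will be made.

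Three details need settling.

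- **Other events.** If TEAEs and ADRs are also shown by dose, use one equal post-dose window for all four doses, cut off at the next dose, or report events per person-time. Do not assign events to the most recent dose. Visit windows move the real gaps (the first can be as short as 14 − 5 = 9 days), so show the days at risk.
- **Incomplete onset dates.** Flag these events separately instead of assigning them to a dose through the SAP 4.3 rule.
- **Onset recorded as a date only.** Protocol 7.4.3 lists start dates, not times. If no time is recorded, state how the 24-hour definition is applied, for example as onset on the dosing day or the day after.

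The cost is one or two extra tables from data already collected, with no change to conduct. Cells will be small: at most 12 subjects per dose, so that no reactions in 12 still allows a true rate of up to 26.5%.

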### (2) Laboratory tests (hematology/ blood chemistry/urinalysis tests)

Laboratory tests shall present descriptive statistics (number of subjects, mean, standard deviation, median, minimum, maximum) for the quantity of change at each visit (DAY 14, DAY 90, DAY 104, DAY 180, DAY 270) compared with the measurement values of each visit and the baseline (DAY 0). The difference at each visit compared with the baseline shall be analyzed using a paired t-test (Wilcoxon's signed rank test if Shapiro-Wilk test results do not satisfy normality).

The rate of change for the clinically significant abnormalities (Normal / NCS [Not Clinically Significant Abnormal] / CS [Clinically Significant Abnormal]) at each visit (DAY 14, DAY 90, DAY 104, DAY 180, DAY 270) compared with the baseline (DAY 0) shall be summarized as frequencies and percentages and presented as a contingency table. The difference at each visit compared with the baseline shall be analyzed using the McNemar-Bowker's test. In addition, a detailed list shall be presented for clinically significant abnormal results.

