In order not to miss the occurrence of adverse events which the investigator does not know about, all methods such as phone calls, letters, and direct visits shall be utilized to directly contact the subjects who refuse to visit. The reasons for early discontinuation or termination of administration shall be recorded in the case report form. Subjects who have early discontinued or have terminated administration may not participate again.

For subjects who have early terminated the study, the tests for early termination in "Summary of Study Schedule" shall be performed.

If the clinical study has been early discontinued, the following shall be performed:

- 1) If the principal investigator has early terminated or suspended the clinical study without a prior agreement with the sponsor, the principal investigator shall immediately inform this fact to the sponsor and the Institutional Review Board, and shall submit a detailed statement of reasons for the early termination and suspension.
- 2) If the sponsor has early terminated or suspended the clinical study, the principal investigator shall immediately inform this fact to the Institutional Review Board, and shall submit a detailed statement of reasons for the early termination and suspension.
- 3) If the Institutional Review Board has early terminated or suspended the clinical study, the principal investigator shall immediately inform this fact to the sponsor, and shall submit a detailed statement of reasons for the early termination and suspension.
- 4) If the relevant clinical study has been early terminated or suspended as in 1) through 3) in accordance with regulations, the principal investigator shall immediately inform this fact to the subjects, and shall ensure that appropriate measures are taken and follow-ups are conducted.

[figure not shown]
For subjects who have been discontinued due to adverse events, follow-ups shall be conducted until the investigator determines that the corresponding adverse events are resolved or the subjects are medically stable. For these subjects, Helixmith Co., Ltd. and the investigators shall try their best to provide standard clinical treatment. Helixmith Co., Ltd. shall provide indemnification, if applicable, in accordance with the subject indemnification policy. In addition, the tests (10 items) mentioned above shall be performed for the safety of the subjects.

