6.1.9 Unscheduled Visits

Adverse event assessment

Information on newly developed or worsened adverse events, or adverse events that disappeared since the last visit shall be collected.

Complete blood cell count

This shall be performed at Visit 1 and throughout the clinical study every time a subject makes a visit (shall be performed prior to administering the investigational product at Visits 2, 3, 4, and 5). However, if there is a subject with abnormal findings in the test at Visit 3 (Day 14), a complete blood cell count and a general blood chemistry test may be performed at Day 30 depending on the decision of the principal investigator. The complete blood cell count items are as follows:

WBC, RBC, Hb, Hct, MCV, MCH, MCHC, PLT, ESR, MPV, differential count of WBC (Band neutrophil, Segmented neutrophil, Basophil, Lymphocyte, Monocyte)

General blood chemistry test

This shall be performed at Visit 1 and throughout the clinical study every time a subject makes a visit (shall be performed prior to administering the investigational product at Visits 2, 3, 4, and 5). However, if there is a subject with abnormal findings in the test at Visit 3 (Day 14), a complete blood cell count and a general blood chemistry test may be performed at Day 30 depending on the decision of the principal investigator. Since a blood glucose test is included, the subject shall maintain an 8-hour fasting state prior to the test. The general blood chemistry test items are as follows:

total protein, albumin, globulin, A/G ratio, cholesterol, total bilirubin, AST, ALT, fasting glucose, BUN, creatinine, estimated GFR, Ca²⁺, phosphate, Na⁺, K⁺, Cl⁻, CRP, triglyceride, HDL-cholesterol, LDL-cholesterol

Body measurement (weight measurement)

A subject's weight shall be measured at Visit 1 and throughout the clinical study every time a subject makes a visit (shall be performed prior to administering the investigational product at Visits 2, 3, 4, and 5).

Urinalysis with microscopy

This shall be performed at Visit 1 and throughout the clinical study every time a subject makes a visit (shall be performed prior to administering the investigational product at Visits 2, 3, 4, and 5). However, if there is a subject with abnormal findings in the test at Visit 3 (Day 14), urinalysis with microscopy may be performed at Day 30 depending on the decision of the principal investigator.

The urinalysis items are as follows:

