#### (3) Vital signs

Vital signs shall present descriptive statistics (number of subjects, mean, standard deviation, median, minimum, maximum) for the quantity of change prior to administration at each visit (DAY 14, DAY 90, DAY 104, DAY 180, DAY 270) compared with the measurement values prior to administration at each visit and the baseline (DAY 0). The difference at each visit compared with the baseline prior to administration shall be analyzed using a paired t-test (Wilcoxon's signed rank test if Shapiro-Wilk test results do not satisfy normality).

The rate of change for the clinically significant abnormalities (Normal / NCS [Not Clinically Significant Abnormal] / CS [Clinically Significant Abnormal]) at each visit (DAY 14, DAY 90, DAY 104, DAY 180, DAY 270) compared with the baseline (DAY 0) prior to administration shall be summarized as frequencies and percentages and

presented as a contingency table. The difference at each visit compared with the baseline prior to administration shall be analyzed using the McNemar-Bowker's test.

In addition, descriptive statistics (number of subjects, mean, standard deviation, median, minimum, maximum) shall be presented for the pre-/post-administration measurement values at each visit and the quantity of change for pre-administration versus post-administration. The differences between pre-administration and post-administration shall be analyzed using a paired t-test (Wilcoxon's signed rank test if Shapiro-Wilk test results do not satisfy normality).

The rate of change for the clinically significant abnormalities (Normal / NCS [Not Clinically Significant Abnormal] / CS [Clinically Significant Abnormal]) of pre-administration versus post-administration shall be summarized as frequencies and percentages and presented as a contingency table. The differences between pre-administration and post-administration shall be analyzed using the McNemar-Bowker's test.

A detailed list shall be presented for clinically significant abnormal results.

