#### 4.8 Efficacy Assessment

#### (1) Severity of disease

: The descriptive statistics (number of subjects, mean, standard deviation, median, minimum, maximum) for each item of CMTNS-v2 at the termination visit (DAY 270) compared with the baseline (DAY 0) shall be presented, and the differences at the termination visit compared with the baseline shall be analyzed using a paired t-test (Wilcoxon's signed rank test if Shapiro-Wilk test results do not satisfy the assumption of normal distribution). In addition, descriptive statistics (frequency, percentage) shall be presented for changes in the total score, and a contingency table shall be prepared for the pre-/post-administration differences, and analysis shall be performed using the McNemar-Bowker's test.

In addition, descriptive statistics (number of subjects, mean, standard deviation, median, minimum, maximum) shall be presented for the changes in FDS at each visit (DAY 90, DAY 180, DAY 270) compared with the baseline (DAY 0), and analysis shall be performed using a paired t-test (Wilcoxon's signed rank test if Shapiro-Wilk test results do not satisfy the assumption of normal distribution) for the differences at each visit compared with the baseline.

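### SAP 4.7 tabulates laboratory and vital-sign change and shift at five planned days only, so results short of clinically significant from Day 30, early-termination and unscheduled visits reach no planned table or listing

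*SAP*

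**What the plan says.** Laboratory tests and vital signs are part of the primary endpoint (Protocol 6.2 and 8.4.3), listed separately from adverse events.

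**Collection.** The schedule in Protocol 6.1 marks blood tests, urinalysis and vital signs after baseline at Days 14, 30, 90, 104, 180 and 270, at early termination and at unscheduled visits. Day 30 takes place only if the principal investigator asks for it after abnormal Day 14 findings (6.1.4). Protocol 5.5.3 covers leavers: "For subjects who have early terminated the study, the tests for early termination in" the schedule are to be done. Protocol 6.1.9 repeats for unscheduled visits: "This shall be performed at Visit 1 and throughout the clinical study every time a subject makes a visit".

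**Analysis.** Protocol 8.4.3(2) asks for descriptive statistics and Normal/NCS/CS shifts by visit and names no days. The SAP narrows this. SAP 4.7(2) covers "the quantity of change at each visit (DAY 14, DAY 90, DAY 104, DAY 180, DAY 270"). SAP 4.7(3) covers "the quantity of change prior to administration at each visit (DAY 14, DAY 90, DAY 104, DAY 180, DAY 270"). The shift tables in both subsections repeat the five days. Each subsection also calls for a CS listing with no visit restriction: "In addition, a detailed list shall be presented for clinically significant abnormal results" for laboratory tests and "A detailed list shall be presented for clinically significant abnormal results" for vital signs.

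**The concern.** The five-day list leaves out the visits that exist because something departed from plan. For Day 30 the protocol says so directly, since an abnormal Day 14 finding triggers it. For early termination and unscheduled visits it is a reasonable inference and no more.

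Two things are at stake. First, post-dose measurements of a primary endpoint are collected and then given no place in the output unless someone grades them CS. Second, the plan never produces the simplest summary of a laboratory or vital-sign parameter: how many treated subjects moved to a worse category at any time after dosing. Separate by-visit tables cannot supply it, because an abnormal result at Day 14 and another at Day 90 may belong to one subject or to two.

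**Working it through.** No figure in the plan depends on this point, so the check sets collection against output.

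**Step 1. Count the occasions.** Post-baseline columns with laboratory tests and vital signs in the Protocol 6.1 schedule: Day 14, Day 30, Day 90, Day 104, Day 180, Day 270, early termination, unscheduled = 8. Days named in SAP 4.7(2) and (3): 14, 90, 104, 180, 270 = 5. Not named: 8 − 5 = 3 (Day 30, early termination, unscheduled).

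**Step 2. Look for a rule that brings the three back in.** SAP 4.3 leaves values missing through early termination unimputed and analyses what is available. It does not assign an off-schedule result to a visit. The SAP has no visit windows and no worst-post-baseline summary. SAP 3.2(3) mentions the Day 30 vital-sign follow-up, but 4.7(3) gives it no row. The second set of vital-sign tables, which "shall be presented for the pre-/post-administration measurement values at each visit", adds readings taken after injection on dosing days, including Day 0. No dose is given at the three missing visits, so those tables do not reach them.

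**Step 3. Trace each kind of result from the three visits.**

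| Result | Change and shift tables | CS listing | TEAE tables |
|---|---|---|---|
| CS | no | yes | yes, once recorded as an AE |
| NCS | no | no | not by definition |
| Normal, but moved numerically | no | no | no |

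The last column rests on the adverse-event definitions in Protocol 7.1 and SAP 3.2(1), which take in clinically meaningful laboratory abnormalities. It also rests on adverse-event collection at Day 30, early termination and unscheduled visits (Protocol 6.1.4, 6.1.8, 6.1.9), and on SAP 4.7(1), which is not tied to planned days.

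**Step 4. See what each part of a remedy recovers.**
- *Day 30.* The triggering parameter was already abnormal at Day 14, so it is in the Day 14 row. A worst-category table changes for that parameter only if it goes from NCS to CS, and a CS result is listed anyway. What is missing is whether the finding persisted or resolved, and only a listing of the Day 30 values shows that.
- *Early termination and unscheduled visits.* A new NCS shift may have no counterpart at a named day. The worst-category table captures it.

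**Step 5. Size.** The documents give no counts for these visits, so the number of results affected is unknown. If all 12 subjects enter the Safety Set, each subject whose worst category is seen only off schedule moves an any-visit incidence by 1/12 = 8.3 percentage points.

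**The case against.** A reader might infer that results from these visits enter no primary safety summary at all. The documents do not support that. The CS listings have no visit limit, Protocol 8.4.3(2) also asks for a list of subjects graded CS, and a clinically significant abnormality is an adverse event that SAP 4.7(1) counts with a percentage and an exact interval. Adverse events are themselves a primary safety item.

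A reader might also infer that the by-visit tables are biased toward normal. That too goes further than the text. The Day 14 result that triggers Day 30 is tabulated. Subjects may leave by their own decision, through loss to follow-up, or for administrative or COVID-19 reasons (Protocol 5.5.2, 5.5.3, 5.7.2), so an early-termination visit need not signal a safety problem.

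Keeping by-visit tables to planned days is sound practice, because off-schedule visits have few, selected subjects and no common time point. With 12 subjects, complete listings are also easy to read. Finally, Protocol 6.1.8 describes Visit 7 and early termination under one heading, so early-termination data might be filed under Day 270. The schedule gives them separate columns, however, and the SAP does not say to merge them.

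What stands after all this is the NCS and numeric material, and the missing any-visit incidence. The adverse-event tables do not replace either: Protocol 7.4.3 tells the investigator to record an overall diagnosis in place of individual signs, so those tables do not work parameter by parameter, and a CS listing carries no denominator.

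**Conclusion.** The point holds for the change and shift tables. Three of eight post-baseline collection occasions have no row there. NCS shifts and numeric changes from those occasions have no planned table or listing, and no any-visit shift incidence over the Safety Set is planned. CS results are not lost. This is a modest, specific gap in a primary safety summary, and its effect on reported rates cannot be sized from the documents. It assumes that the five-day list will be programmed as written and that no separate output specification adds the other visits.

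The point does not extend to efficacy. SAP 4.8 likewise names planned days, for example "the changes in FDS at each visit (DAY 90, DAY 180, DAY 270) compared with the baseline (DAY 0"), and a reader might infer that the early-termination score should stand in as a last value. That would mix unequal follow-up times and come close to carrying values forward, whereas the plan chose not to impute (Protocol 8.2, SAP 4.3). No change to 4.8 is called for on this ground.

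**What to change.** Keep the by-visit tables in SAP 4.7(2) and (3) as they are, and add to each subsection:

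1. For each parameter, a shift table from the Day 0 pre-dose category to the worst category recorded at any visit after the first dose, with Day 30, unscheduled and early-termination visits included and the Safety Set as denominator. For vital signs, state whether the readings taken on dosing days after injection count.
2. A listing of all laboratory and vital-sign values from Day 30, unscheduled and early-termination visits, whatever their grade, with the study day and the change from Day 0.

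The cost is SAP wording plus one table and one listing per domain. The data are already collected, and no visit, test or clinical procedure changes.
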